Research in a range of occupational settings has indicated that resilience plays an important role in ameliorating the impact of adverse events in high pressure environments. This project will use a randomised controlled trial research design to assess the efficacy of brief one-to-one Acceptance and Commitment Training (ACTr), designed to enhance surgeons' psychological resilience. According to acceptance and commitment therapy (Hayes, 2004), psychological flexibility is implicated in psychopathology. Psychopathology is primarily the consequence of psychological inflexibility i.e. inability to persist or change behaviour according to long-term values due to language and cognition skills (Hayes, 2006), which has particular significance when an individual is confronted with stress or adversity.

2: Aims and Objectives

The main aim of our research is to assess the efficacy of a brief Acceptance and Commitment Training course. We wish to ascertain whether such a course can increase surgeons' resilience by increasing psychological flexibility, valuing and self-compassion (all of which are expected to be positively impacted by this training). This research will fill a gap in the relevant research literature; namely that no research project as far as we are aware has evaluated ACTr as a means to enhance resilience in surgeons. In fact any research conducted on resilience training with a surgical population is rare.

3: Design

The proposed study will initially take the shape of a small pilot study (n=10) and following this a randomised controlled trial. (n=100)

The intervention will consist of Acceptance and Commitment Training (ACTr), on a 1:1 basis. Flaxman (2013) devised a workplace training program which will form the basis of this training protocol. ACT as a workplace training has been supported by numerous studies including Lappalainen et al (2007), Finnes and Ghaderi (2017). A recent manual, Flaxman, Bond and Livheim (2013), will be utilised for this study, with a bespoke tailoring to the surgeons' population. See section 12 for full details.

4: Participants

Trainee surgeons and consultant surgeons from local hospitals, initially Royal Bournemouth Hospital, Bournemouth, Dorset; and Poole Hospital, Poole, Dorset. Then the John Radcliffe Hospital, Oxford; Southampton General Hospital, Southampton and Portsmouth General Hospital.

5: Sampling

Strategy

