Block randomisation (blocks of 4) will be used to help ensure equal-sized groups. An external statistician will generate random blocks of 4.

Sample Size

For the RCT, we intend to recruit 100 to allow for some attrition and still have approximately 45 participants per condition. This number is based on previous studies(e.g Flaxman and Bond, 2010) conducted using ACTr based training; this will give enough statistical power, particularly with regards to mediation analysis.

6: Recruitment

Recruitment will initially be through Royal Bournemouth Hospital and will be initiated by [name], MA DM FRCS(Urol) (Principal Investigator). An invitation email will be sent to potential participants (again identified by [name]) and further information regarding the study will be forwarded to the potential participant on their request only.

7: Randomisation

Participants will be allocated one of two groups, the experimental group (who will receive ACTr) or the wait-list control group. Participants allocated to the wait-list control will be offered the same ACTr sessions once the current study has ended.

8: Data Collection

Data Collection Points

T1 – 2 Weeks before training session one. Via email/on-line questionnaires.

S1- First training session

Interval (4 weeks RCT, 2 weeks Pilot)

T2 – Immediately before the beginning of training session two.

S2 – Second Training session

Interval (4 weeks RCT, 2 weeks Pilot)

T3 - Immediately before the beginning of training session three.

S3 – Third Training session

T4 –Within two week of completion of training session three.

T5- Follow-up, 12 weeks after training session three. Via email.

Primary Outcome Measures

Resilience - Brief Resilience Scale (BRS)

General Health - General Health Questionnaire (GHQ-12)

Secondary Outcome and Process Measures

CBI (Copenhagen Burnout Inventory)

DASS21 (Depression Anxiety and Stress Scale)

VLQ (Value Living Questionnaire)

WAAQ (Work related Acceptance and Action Questionnaire)

AAQII (Acceptance and Action Questionnaire)

SCS (Self Compassion Scale)

SPS (Sense of Preparedness Scale)

9: Data Analysis

[figure not shown]

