Data will be analysed on an intention-to-treat basis. For the pilot study a series of analyses of variance with time (1-5) as a within-subjects factor will be employed to examine changes in outcome and process measures. For the RCT, a series of analyses of variance will be conducted with time(1-5) as a within-subjects factor and condition (treatment vs control) as a between-subjects factor.

Mediation analysis based on regression will be used to test the role of study processes to ascertain whether outcome measure changes are mediated by process measures.

Furthermore the Jacobson and Truax (1991) method of assessing change for each individual participant will be used in both the pilot and the RCT studies. This will be used to determine whether the magnitude of change for a given client is statistically reliable.

CONSORT 2010 Flow Diagram

Data collected will be presented and analysed descriptively. The consort flow diagram (2010, figure 1.) will be followed to document relevant recruitment data.

Figure 1 (Consort 2010 Flow Diagram)

10: Ethical Considerations

Ethical approval will be sought from the university ethics team and the Integrated Research Application System (IRAS). The researcher will undertake 'Good Clinical Practice' training. Informed consent will be gained at the time of recruitment and verbally prior to the start of each session. Participants will be made aware of their right to withdraw at any time. In the highly unlikely event that participants experience an unexpected uncomfortable response during the session, emotional 'grounding techniques' will be utilised by the trainer. Furthermore, Clinical Psychologist [name] (Chief Investigator) contact details will be made available to participants, as will details of the BMA's Doctors for Doctors website and helpline (who can offer ongoing counselling).

11: Data Protection and Storage

Recordings

Training sessions will be recorded as a further safeguard and assessment tool. The only purpose of recording the sessions is to ensure the ACTr process is being delivered accurately and correctly. Randomly selected section of sessions will be assessed by an independent ACTr assessor ([name] will source the assessor and this will be kept on file) to rate fidelity to the established ACTr protocol. If, a randomly selected recording identifies the participant or anyone else, it will NOT be forwarded to the independent assessor, and another recording will be randomly selected.

Data

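### Two unranked primary scales, no stated success rule and no primary time: the planned five-occasion ANOVA does not isolate the effect of the completed course on resilience

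*Protocol*

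**What the plan says.** Protocol Section 2 sets a general aim, the efficacy of a brief ACTr course, and then a specific one: whether the course can raise surgeons' "resilience by increasing psychological flexibility, valuing and self-compassion (all of which are expected to be positively impacted by this training". General health is not mentioned in the aims.

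Protocol Section 8 lists two primary outcome measures at the same level, "Resilience - Brief Resilience Scale (BRS" and "General Health - General Health Questionnaire (GHQ-12". The occasions after the T1 baseline are:

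- T2: "Immediately before the beginning of training session two"
- T3: "Immediately before the beginning of training session three"
- T4: "Within two week of completion of training session three"
- T5: "T5- Follow-up, 12 weeks after training session three. Via email"

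None of these is named as the primary time.

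For the RCT, Section 9 states that "a series of analyses of variance will be conducted with time(1-5) as a within-subjects factor and condition (treatment vs control) as a between-subjects factor". It does not say which term of that model (condition, interaction or a contrast) carries the efficacy conclusion. The sample-size text in Section 5 aims for about 45 per condition and ties its power statement to no scale and no occasion.

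**The concern.** Two things are left open that together define what a positive trial means.

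**Scale.** With two equal primaries and no success rule, a trial with a GHQ-12 effect and no BRS gain has no agreed interpretation. It could be presented as a positive primary result, although the resilience question in Section 2 would then be unanswered.

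**Time.** The interaction over T1 to T5 tests for any difference in profile between the arms. At T2 one session has been given and at T3 two; only T4 and T5 follow the whole course. A difference confined to T2 and T3 is enough to make the interaction significant. The stated test therefore does not target the quantity of interest, the arm difference after the completed course.

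At stake is whether the headline result answers Section 2, and whether the choice of scale and occasion is made before or after the data are seen.

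**Working it through.** **The plan's own figure.** 100 recruited with 10% loss gives 100 × 0.90 = 90, or 45 per arm, which agrees with Section 5. The size itself cannot be reproduced, because no alpha, power, effect size, SD, scale or occasion is given.

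**Assumptions (not in the Protocol).** Two-sided 5% per test; equal correlation ρ between occasions; SD 1 at each occasion; effects in SD units.

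**1. Two scales.** Under no effect on either scale, the chance that at least one of two 5% tests is significant is:

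- independent: 1 − 0.95² = 9.75%
- test statistics correlated 0.5 (bivariate normal): 9.1%
- correlated 0.7: 8.3%

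A simulation of the five-occasion interaction test itself, with scale correlations of 0 to 0.7, gave about 8.6% to 10%. All of these presuppose that success on either scale suffices. If both must succeed, the chance of a false claim is at most 5%.

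**2. What the interaction test responds to.** For arm differences δ₁…δ₅ and n per arm, the F test on 4 and 4(2n − 2) degrees of freedom has noncentrality λ = (n/2) Σ(δₜ − δ̄)² / (1 − ρ). With n = 45 the degrees of freedom are 4 and 352, and the 5% critical value is 2.40.

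Take δ = (0, 0.4, 0.4, 0, 0), an effect at T2 and T3 that is absent at T4 and T5. Then δ̄ = 0.16, the sum of squares is 2 × 0.24² + 3 × 0.16² = 0.192, and λ = 22.5 × 0.192 / (1 − ρ) = 4.32 / (1 − ρ).

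| ρ | λ | Chance that the interaction is significant |
|---|---|---|
| 0.5 | 8.64 | 64% |
| 0.6 | 10.8 | 75% |
| 0.7 | 14.4 | 87% |

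With 0.3 SD in place of 0.4 SD and ρ = 0.6, the sum of squares is 0.108, λ = 22.5 × 0.108 / 0.4 = 6.075, and the chance is 47%.

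**3. Power of a single post-course contrast.** Assume 0.5 SD and 45 per arm.

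- Unadjusted: noncentrality 0.5 × √(45/2) = 2.37, power about 65%.
- Adjusted for baseline at ρ = 0.6: residual variance 1 − 0.6² = 0.64, noncentrality 0.5 × √(22.5 / 0.64) = 2.96, power about 83%.
- For comparison, the planned interaction with 0.5 SD sustained from T2 to T5 and ρ = 0.6: δ̄ = 0.4, sum of squares 0.4² + 4 × 0.1² = 0.20, λ = 22.5 × 0.20 / 0.4 = 11.25, power about 77%.

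**The case against.** A reader might infer that the Protocol lets a positive result on either scale, at any time, count as efficacy. It does not say so. No success rule is given, so requiring both scales is an equally open reading, and under it the 8-10% figure does not arise. Section 9 puts all occasions in one model per measure, with no separate tests by occasion, and does not say that a significant interaction alone establishes efficacy. The T4 and T5 means would be in the same analysis, and reporting them would show a passing effect for what it is. This objection stands: the Protocol leaves the rule open and does not state a lax one.

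A reader might also infer that GHQ-12 has no place as a primary outcome. That goes too far. Section 2 opens with efficacy in general, and the background connects psychological flexibility with psychopathology. What is at fault is the lack of ranking.

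The mid-course pattern is hypothetical: nothing in the Protocol suggests that an effect would vanish just as the course is completed. The 64-87% is the power of the test against that pattern, so it cannot be read as a false-positive rate.

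Nor do the documents single out T5 over T4, since both follow the completed course. T5 is collected by email and is the latest occasion, so it may be the more exposed to attrition.

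Finally, multiplicity mechanics and model details may sit in a statistical analysis plan that is not at hand. That excuses the absence of those details. It does not remove the point, because the Protocol itself fixes two equal primaries and an all-occasions test, and a later document that chose one scale and one time would be changing what the Protocol set.

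**Conclusion.** The point holds in limited form. Section 8 names two unranked primaries with no success rule and no primary time, and the omnibus test in Section 9 does not by itself show that the completed course raised resilience.

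On scale, the size is a false-positive chance of about 8-10% against a nominal 5%, conditional on an assumed either-scale reading and 5% per test. On time, the 64-87% shows only how readily the test responds to a mid-course difference, and it rests on the assumed 0.4 SD effect, equal correlations of 0.5-0.7 and 45 per arm.

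This should be corrected. It does not establish that the trial would reach a wrong conclusion, because the Protocol does not commit to calling a mid-course or GHQ-12-only result efficacy.

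**What to change.** **Section 8.** Make BRS the lead primary, since it measures the resilience named in Section 2. Test GHQ-12 at 5% only if BRS succeeds; this fixed sequence holds the overall error at 5%. Alternatively, keep both as primaries and state that both must succeed. Name one post-course target in advance: T4, T5 or their average. The sponsor should choose.

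**Section 9.** Base the efficacy claim on the arm difference in BRS at that target, adjusted for T1 BRS. Keep the five-occasion ANOVA, and T2 and T3 in particular, for trajectory and mediation.

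**Cost.** The change is to wording; it needs no further data or participants. A result on GHQ-12 alone, or at mid-course alone, would no longer count as efficacy. The baseline adjustment is essential: under the assumptions above, an unadjusted single-occasion contrast (about 65% power) would do worse than the planned interaction under a sustained effect (about 77%), whereas the adjusted contrast (about 83%) would not.

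### Section 9 promises intention-to-treat, but the five-wave ANOVA it names, as usually run, drops anyone missing one questionnaire, and two of the five waves are tied to training sessions

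*Protocol*

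**What the plan says.** Section 9 sets the principle, "Data will be analysed on an intention-to-treat basis", and in the same paragraph the RCT method: "a series of analyses of variance will be conducted with time(1-5) as a within-subjects factor and condition (treatment vs control) as a between-subjects factor".

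Section 5 foresees loss. The aim is to "recruit 100 to allow for some attrition and still have approximately 45 participants per condition".

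Section 8 lists five waves:
- T1, two weeks before session one: "Via email/on-line questionnaires".
- T2: "Immediately before the beginning of training session two".
- T3: "Immediately before the beginning of training session three".
- T4: within two weeks of session three, with no mode of collection given.
- T5: "Follow-up, 12 weeks after training session three", by email.

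The section 12 timetables for sessions two and three each open with an 8.45 data-collection slot. Under section 7, wait-list controls are offered sessions only after the study ends. Section 8 does not say how their T2 and T3 are collected.

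**The concern.** A conventional repeated-measures ANOVA needs every score from every person. A standard software routine given data with one missing cell stopped with an unbalanced-data error. Unless scores are imputed, the analysis set is the completers and not everyone randomised.

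The design can link completeness to arm and attendance. An ACTr participant who stops coming is likely to miss T2 or T3, and one missed wave discards that person's T5 as well. Controls have no sessions to miss. If ACTr alone loses its poor responders, the comparison on the primary outcomes (BRS and GHQ-12) tilts towards ACTr, which is what intention-to-treat is meant to prevent. If loss is unrelated to response, the cost is power alone.

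The point is the method the protocol names, not the absence of a missing-data section, which an SAP may hold.

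**Working it through.** **The protocol's own allowance.** 100 recruited and about 45 per condition kept gives 90/100, an implied loss of 10%. The protocol states no alpha, power, effect size or SD, so there is no power figure to reproduce.

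**How many people are complete.** If a share m misses each of the four follow-up waves independently, complete cases = 100 × (1 − m)^4:
- m = 2.5%: 100 × 0.975^4 = 90.4
- m = 5%: 100 × 0.95^4 = 81.5
- m = 10%: 100 × 0.90^4 = 65.6

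Keeping 90 complete requires m ≤ 1 − 0.9^(1/4) = 2.6% per wave. The values of m are assumptions.

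**Simulation set-up (all assumed).** 50 per arm; assessments at weeks −2, 4, 8, 9 and 20 from session one; 3,000 trials per setting. Three correlation structures were used: constant 0.6; exp(−gap/30 weeks); 0.4 + 0.4 exp(−gap/12 weeks). Ranges below run over the three. The ANOVA is the Greenhouse-Geisser-corrected condition-by-time test on complete cases, and bias is the arm difference in T1-to-T5 change. The comparator is a maximum-likelihood model with unstructured covariance, a common T1 mean and a joint 4-df test of the T2-T5 arm differences. With no loss and no effect, the false-positive rate is 4.6-5.2% (ANOVA) and 4.8-5.4% (model). Monte Carlo error is about 0.4 points at 5% and 0.004 SD for bias.

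**No true effect, people stop before session three (T3-T5 missing), complete-case ANOVA.**

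| Mechanism | Loss | Bias at T5 | False positives |
|---|---|---|---|
| (a) same in both arms | 10-20% | under 0.01 SD | 3.5-5.3% |
| (b) ACTr only, odds of leaving double per SD worse T1-T2 gain | 10% | 0.02-0.04 SD | about 5% |
| (b) | 20% | about 0.06 SD | 5-7% |
| (c) ACTr only, all the worst gainers leave (extreme) | 10% | 0.09 SD | 8-9% |
| (c) | 20% | 0.15-0.16 SD | 15-22% |

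In (a)-(c) the likelihood model has bias under 0.01 SD and 4-6% false positives.

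**Hand check of (c), constant correlation 0.6.** The SD of the T1-T2 gain is √(2 × 0.4) = 0.894. Removing the worst 10% raises the mean gain by 0.894 × 0.1755/0.9 = 0.174, where 0.1755 is the normal density at the 10% point. The slope of T1-T5 change on that gain is 0.4/0.8 = 0.5, so the bias is 0.5 × 0.174 = 0.087 SD. The simulation gave 0.088.

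**(d) Leaving depends on the unseen T5 gain, ACTr only, 10-20% loss.** Bias is 0.05-0.14 SD for the ANOVA and still 0.04-0.09 SD for the model. If the same people miss only T3, and T4 and T5 are obtained by email, the ANOVA still drops them (0.06-0.14 SD), while the model's bias is under 0.005 SD.

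**Power with no selective loss, assumed 0.5 SD effect at T2-T5.**

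| Missing per follow-up wave | ANOVA | Likelihood model |
|---|---|---|
| none | 76-87% | 89-96% |
| 2.5% | 72-83% | not tabulated |
| 5% | 64-78% | 88-95% |
| 10% | 54-65% | 87-95% |

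The model's lead in the first row comes from baseline adjustment and the joint test, not from missing data. The missing-data effect is the fall down each column: about 22 points for the ANOVA and about 1-2 for the model.

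**The case against.** The protocol nowhere says that incomplete cases are dropped. An unseen SAP could impute before the ANOVA, and the figures above would then change or vanish. This stands as a limit: what is established is a poor fit between stated principle and stated method, not a literal contradiction. But an SAP that simply carries out the named method inherits the problem.

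At the 10% loss the protocol allows for, the harm is small outside the extreme case. The bias in (b), at most 0.04 SD, is about a fifth of the standard error of the T1-T5 arm difference; at constant correlation 0.6 that error is √(0.8 × (1/45 + 1/50)) = 0.18 SD. If the people who leave miss every later wave, 10% loss still leaves 90 complete, as section 5 intends. The larger power losses need 5-10% missing independently at each wave, a rate that no part of the protocol supports or rules out. All of this stands and keeps the point moderate.

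The attendance link is partly inference. Training is one-to-one, so a session might be rebooked; the 8.45 slots sit in timetables offered as examples; and nothing refuses a questionnaire to a non-attender. Even so, T2 and T3 are defined by the sessions, and no other route is given for someone who stops coming.

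The remedy could be narrower: a mixed model keeping the plain condition-by-time test, or imputation before the ANOVA, would also answer the missing-data point. Under randomisation, though, the joint T2-T5 test with a common baseline addresses the same null hypothesis. Finally, section 11 destroys personal data on withdrawal. If that covers scores, it limits what can be kept for formal withdrawers, but not for people who only miss a session.

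**Conclusion.** The concern holds. The named ANOVA, run conventionally, does not deliver the promised intention-to-treat analysis once any wave is missed, and tying T2 and T3 to sessions can make exclusion depend on arm and attendance. The bias may be trivial or serious according to how selective the loss is, and the protocol gives no figure that settles which. The loss of power is the firmer consequence because it needs no selective loss, but its size depends on the assumed missing rate and on the assumed 0.5 SD effect. Everything is conditional on no imputation. The point is worth correcting because the correction is cheap, not because the trial would otherwise certainly mislead.

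**What to change.** **Section 9.** Replace the RCT ANOVA with a likelihood-based mixed model for repeated measures that uses all observed scores of every randomised participant in the allocated arm. Treat T1 as an outcome with a common mean in both arms, and test the arm differences at T2-T5 jointly. Add one missing-not-at-random sensitivity analysis, for example shifting unobserved ACTr scores in the unfavourable direction. Covariance structure and shift sizes can be left to the SAP. State whether the section 11 rule on withdrawal covers questionnaire scores already collected.

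**Section 8.** Send T2-T5 by email to controls and to anyone who misses a session, at the calendar times the stated intervals already imply. Counting from T1, these are 2 + 4 = 6 weeks (T2), 6 + 4 = 10 (T3), by 10 + 2 = 12 (T4) and 10 + 12 = 22 (T5).

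The two changes belong together. Scenario (d) shows that the model alone leaves bias when T5 is lost, and that the ANOVA ignores T5 even when it is obtained.

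**Cost.** Wording changes in two sections, somewhat more analysis work and some emailed questionnaires; no extra participants or visits.

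### The five-level ANOVA treats pre-training T1 as an outcome level; adjusting for T1 would estimate every later arm difference more precisely, at no cost in data

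*Protocol*

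**What the plan says.** Protocol section 9 fixes the model for the randomised trial: "a series of analyses of variance will be conducted with time(1-5) as a within-subjects factor and condition (treatment vs control) as a between-subjects factor". It names no covariate.

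Section 8 defines the five times. T1 is "2 Weeks before training session one". T2 is "Immediately before the beginning of training session two", and T3 stands in the same relation to session three. T4 is "Within two week of completion of training session three" and T5 is "Follow-up, 12 weeks after training session three". The primary outcomes are BRS and GHQ-12. Section 8 does not say whether T1 is answered before or after allocation.

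Section 2 gives the purpose: "The main aim of our research is to assess the efficacy of a brief Acceptance and Commitment Training course". Section 5 expects "approximately 45 participants per condition" after attrition from 100 recruited. It gives no effect size, standard deviation or correlation.

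**The concern.** T1 cannot carry a training effect. Its value lies in explaining differences between surgeons that exist before the course. A five-level time factor with an unconstrained mean for each arm at T1 does not use it fully. In that model, an arm difference at a later visit is either the difference in change from T1, which subtracts T1 with a slope fixed at 1, or the difference at that visit alone, which is a slope fixed at 0. Adjustment estimates the slope from the data.

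At stake is precision on the two primary outcomes of a fairly small trial. Ease of interpretation is also affected. If the test is taken as the condition main effect, T1 is averaged into the arm difference. If it is taken as the 4-degree-of-freedom interaction, the F statistic alone gives neither direction nor timing. The protocol does not say which term is meant, and a statistical analysis plan may settle that, so the silence is not the point here.

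**Working it through.** **Inputs from the protocol.** About 45 per arm (section 5). Visit times in weeks from T1 (section 8): T1 0, T2 2 + 4 = 6, T3 6 + 4 = 10, T5 10 + 12 = 22. T4 falls within two weeks of session three and is taken as week 11. The attrition arithmetic agrees: 100 × 0.90 = 90, or 45 per arm. There is no stated power calculation to reproduce.

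**Assumed.** SD 1 at each visit, two-sided 5% level, and seven correlation structures:
- equal correlation (CS) of 0.5, 0.6 and 0.7;
- exponential decay r^(weeks/10) with r = 0.6 and 0.7;
- a mixture w + (1 − w) × 0.4^(weeks/10) with w = 0.3 and 0.5.

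**Step 1: algebra.** Let v be the variance of the T4-T5 mean and c its covariance with T1. Per-participant variances are:
- T1 as covariate: v − c²
- change from T1: v + 1 − 2c
- T1 ignored: v

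Change minus covariate is (1 − c)². Ignored minus covariate is c². Neither can be negative, and no treatment effect enters. The same holds jointly. With **r** the vector of correlations of T2 to T5 with T1, the covariance matrix of the four changes exceeds that of the four adjusted responses by (1 − **r**)(1 − **r**)ᵀ, so adjustment never lowers the noncentrality of the joint test. The price is one degree of freedom and a factor 1 + 1/(2n − 4) = 1 + 1/86, about 1.2%.

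**Step 2: numbers for the T4-T5 mean.** Under CS, v = (1 + r)/2 and c = r. For exponential 0.6, the T1-T4 and T4-T5 correlations are both 0.6^1.1 = 0.570 and T1-T5 is 0.6^2.2 = 0.325. So v = (1 + 0.570)/2 = 0.785 and c = (0.570 + 0.325)/2 = 0.448.

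| Structure | v | c | Covariate | Change | Ratio |
|---|---|---|---|---|---|
| CS 0.5 | 0.750 | 0.500 | 0.500 | 0.750 | 0.667 |
| CS 0.6 | 0.800 | 0.600 | 0.440 | 0.600 | 0.733 |
| CS 0.7 | 0.850 | 0.700 | 0.360 | 0.450 | 0.800 |
| Exponential 0.6 | 0.785 | 0.448 | 0.585 | 0.890 | 0.657 |
| Exponential 0.7 | 0.838 | 0.566 | 0.518 | 0.706 | 0.733 |
| Mixture 0.3 | 0.778 | 0.474 | 0.553 | 0.829 | 0.667 |
| Mixture 0.5 | 0.841 | 0.625 | 0.451 | 0.592 | 0.762 |

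Excess variance of change runs from 1/0.800 = 1.25 to 1/0.657 = 1.52, or about 24-50% after the slope cost. To match 45 per arm, change from T1 would need 45/0.800 = 56 to 45/0.657 = 69. The adjusted interval is 1 − √0.800 = 11% to 1 − √0.657 = 19% narrower. Under CS the ratio is (1 + 2r)/3, so the excess is 3/2.6 − 1 = 15% at 0.8 and 3/2.8 − 1 = 7% at 0.9. For a single visit the ratio is (1 + r)/2: 0.75 at r = 0.5 and 0.85 at r = 0.7.

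**Step 3: power for a 0.5 SD difference in the T4-T5 mean** (noncentral t, slope cost included). T1 as covariate 86-97%; change from T1 70-94%; T1 ignored 72-77%.

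**Step 4: a joint example.** Take CS 0.5 with an effect of 0.4 SD at each of T2 to T5. The sum of squared effects is 4 × 0.16 = 0.64. In that direction the variance is 0.5 + 4 × 0.5 = 2.5 for changes and 0.5 + 4 × 0.25 = 1.5 adjusted. The noncentralities are 22.5 × 0.64/2.5 = 5.76 and 22.5 × 0.64/1.5 = 9.60 (9.49 after the slope cost). Power of the multivariate 4-degree-of-freedom test is about 43% and 66%. In other structures and shapes the gain is smaller, sometimes nil, and any loss from the slope cost is a fraction of a point.

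**Step 5: validity.** In simulation under no effect, the Greenhouse-Geisser-corrected interaction rejected in 4.5-5.3%, change from T1 in 4.8-5.3% and the adjusted T4-T5 difference in 4.7-5.2%. With a true T4-T5 difference of 0.40, change and adjusted estimates both averaged about 0.40.

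**The case against.** A time-by-condition ANOVA of a randomised trial is standard and valid. The change-from-T1 contrast is not written in section 9; it is supplied here as a natural way to read an arm difference out of that model. A statistical analysis plan could add a covariate without contradicting the protocol. The gain depends on correlations that the protocol does not give. All of this stands, and it limits the point to an improvement of a valid analysis.

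Three stronger inferences are tempting, and the documents support none of them.

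- *The adjusted T4-T5 difference beats the planned interaction test.* That depends on the effect shape. In simulation over the seven structures, effects at T1 to T5 of 0/0.15/0.30/0.50/0.50 SD put the adjusted T4-T5 difference 11-29 points ahead. A transient 0/0.3/0.5/0.5/0.1 put it 15-33 points behind. The protocol states no expected course, and section 2 fixes no time point, so nothing calls for the T4-T5 average as the main contrast.
- *Keeping T1 among the responses is itself the fault.* A model with T1 as a response and one common T1 mean for both arms is essentially as efficient as adjustment. The loss comes from leaving the T1 means unconstrained.
- *The trial loses a fifth to a third of its participants.* The figures 1 − 0.800 = 20% and 1 − 0.657 = 34% hold only against change from T1 and only at the assumed correlations.

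**Conclusion.** The point holds as one of efficiency, not bias or type I error. For any arm difference after T1, adjustment is at least as precise as change from T1 or ignoring T1, whatever the effect shape and up to about 1% for the slope. For the T4-T5 mean the excess variance of change is about 25-52% in the structures tabulated, 15% at a correlation of 0.8 and 7% at 0.9. At 0.8, power for 0.5 SD is about 99% either way, and the gain is only a slightly narrower interval.

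These sizes assume SD 1, 45 per arm, complete normal data and the listed correlations. No stated sample size or power is shown to be wrong. Like change from T1, adjustment assumes that T1 answers were not affected by knowing the allocation.

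**What to change.** In section 9, for BRS and GHQ-12 in the randomised trial:

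- Analyse T2 to T5 as the responses with T1 as covariate, or keep all five times and constrain the arms to a common T1 mean.
- Test the arm effect jointly over T2 to T5.
- Report the T1-adjusted arm difference with its confidence interval at each visit, including T4 and T5.
- Base any claim of lasting benefit on T5. In simulation with an effect gone by then (0/0.3/0.5/0.5/0 SD), the interaction still rejected in 77-95% of trials, and the adjusted T5 difference in about 5%.

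Making the T4-T5 average the main contrast is an optional trade-off and not part of this change. The cost is wording and one degree of freedom, since T1 is already collected. It would also help to state whether T1 is completed before allocation is known.

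### Does the mediation plan in section 9 build in a false indirect effect because it names no adjustment for T1 scores?

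*Protocol*

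**What the plan says.** Section 9 gives mediation one sentence. The method is stated as "Mediation analysis based on regression will be used to test the role of study processes", and the purpose as "to ascertain whether outcome measure changes are mediated by process measures". It does not state the form of the scores (raw, change or baseline-adjusted), the covariates or the time point of the mediator.

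The main RCT analysis in the same section is a series of analyses of variance with "time(1-5) as a within-subjects factor and condition (treatment vs control) as a between-subjects factor". T1 is thus one level of the time factor there.

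Section 7 randomises condition only: "Participants will be allocated one of two groups". Section 8 places T1 before training ("2 Weeks before training session one. Via email/on-line questionnaires"), so baseline scores will exist for every process and outcome measure.

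Two other places give mediation weight. Section 2 asks whether the course can raise surgeons' "resilience by increasing psychological flexibility, valuing and self-compassion". Section 5 says of the sample size that "this will give enough statistical power, particularly with regards to mediation analysis".

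**The concern.** Randomisation protects the path from condition to process measure and the path from condition to outcome. It does not protect the path from process measure to outcome, because nobody is randomised to a level of psychological flexibility or self-compassion. Surgeons who start high on a process measure may also start high on resilience. On raw later scores, part of that baseline link persists and looks like a process effect. On change scores, regression to the mean can tie the two changes together. The sentence in section 9 could be satisfied by either analysis.

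Mediation is the only analysis in section 9 that speaks to the mechanism named in section 2. A false indirect effect would credit flexibility, valuing or self-compassion with a benefit they did not carry. The power statement in section 5 adds to the unease, because it comes with no effect size, alpha or power.

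**Working it through.** **1. What the text fixes.** It fixes regression as the method and changes in outcome as the target. A regression with T1 process and T1 outcome scores as covariates fits this wording as well as a change-score regression does. A raw-score regression fits it least well, since the stated target is change.

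**2. The model in which the concern bites.** The document gives no correlations, so all inputs except the group size are assumptions. Group size is 45 per arm (section 5). Let ρ be the process-outcome correlation at T1, r the T1-to-later correlation of each measure, and d the effect of training on the process measure in SD. The process has no effect on the outcome. Each later score is r times its own T1 score plus independent noise. The false slope from process to outcome, at ρ = 0.5 and r = 0.6, is:

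- raw: r²ρ = 0.36 × 0.5 = 0.18
- change: (1 − r)ρ/2 = 0.4 × 0.5/2 = 0.10
- both T1 scores as covariates: 0

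Mediation is declared when both paths reach two-sided 5%.

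| Carry-over model, ρ = 0.5, r = 0.6 | raw | change | both T1 covariates |
|---|---|---|---|
| d = 0.5 | 25% | 11% | 4% |
| d = 0.8 | 38% | 15% | 5% |

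At ρ = 0.3 and r = 0.6 the change-score rates fall to 6% (d = 0.5) and 8% (d = 0.8). At ρ = 0 all three analyses stay at 3% to 5%. If training does not move the process measure at all (ρ = 0.5, r = 0.7), none exceeds 4%.

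**3. A second standard model with the same correlations.** Let each score be √r times a stable trait plus √(1 − r) times fresh measurement error, with the two traits correlated at ρ/r = 0.5/0.6 = 0.83. The observed T1 correlation is again 0.5 and the T1-to-later correlation again 0.6. Nothing shared arises after T1, and the process again has no effect on the outcome. The false slopes become:

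- raw: ρ = 0.50
- change: 0, because the trait cancels
- both T1 scores as covariates: ρ(1 − r)² / [1 − r² − 2ρ²(1 − r)] = 0.08/0.44 = 0.18

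| Trait-plus-error model, ρ = 0.5, r = 0.6 | raw | change | both T1 covariates |
|---|---|---|---|
| d = 0.5 | 64–65% | 4% | 32–34% |
| d = 0.8 | 96–97% | 5% | 38–41% |

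Ranges span repeated simulations. At r = 0.7 the T1-covariate analysis gives 19% (d = 0.5) and 21% (d = 0.8). At ρ = 0.3 and r = 0.6 it gives 11% and 13%. Change scores stay at 4% to 6% throughout. The ranking of change scores and T1 covariates therefore reverses between two models that agree on every correlation used in step 2.

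**4. Shared causes after T1.** Return to the carry-over model with ρ = 0.5 and r = 0.6, and let 30% of the later residual variance be shared. The analysis with both T1 covariates then reports false mediation in 67% (d = 0.5) and 81% (d = 0.8) of trials. T1 adjustment does not make the second path safe.

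**5. The power statement.** The section 5 attrition arithmetic is consistent: 2 × 45 = 90, and 90 of 100 implies 10% loss. The power statement cannot be reproduced, because no alpha, effect size or power is given. At assumed path sizes (d of 0.5 or 0.8; process-to-outcome effect 0.3 or 0.4), indirect-effect power at 45 per arm runs from 51% to 92% on raw scores and from 51% to 81% with T1 covariates. That range includes adequate and inadequate values, so it neither confirms nor refutes the statement.

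**The case for a change.** The strongest case for the concern is that the protocol gives mediation real weight: it is the only test of the mechanism in section 2, and section 5 leans on it for the sample size. The wording in section 9 admits analyses whose error rate can be several times 5%, and the baseline scores needed for adjustment are already collected. Adding them would cost two degrees of freedom (87 to 85 in the outcome model at N = 90).

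Much of this stands. The process measures are not randomised, the mechanism of bias is correct, and the step 2 rates reproduce. A raw-score analysis performs badly under both models whenever T1 scores are correlated, and whoever writes the analysis plan should know that.

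Two things do not follow. The protocol does not prescribe the raw-score analysis, and leaving score form and covariates open at this level is ordinary. Nor is it a clear gain to require T1 covariates and bar reliance on change scores. The measures are self-report questionnaires, for which a stable trait measured with error is a plausible description, and there such a rule would exclude the analysis that holds its level in favour of one that does not.

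On power, the statement is indeed bare. But it rests on an earlier study that is not at hand, and no stated figure is missed by the design.

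**Conclusion.** The concern does not hold as a criticism of this protocol. Section 9 names a regression-based mediation analysis of outcome changes and leaves score form and covariates open. That is detail commonly left to a statistical analysis plan, and the text neither states anything wrong nor rules out a sound analysis.

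The size of any bias rests wholly on assumed correlations. At ρ = 0.5, r = 0.6 and d = 0.5, T1 covariates give 4% false mediation under the carry-over model and about 34% under the trait-plus-error model; change scores give 11% and 4%. With no correlations in the document, neither analysis can be called the right one in advance. The bias also requires that training moves the process measure.

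The efficacy question in section 2 is addressed by the time-by-condition analysis of randomised groups, which this point does not touch. The power remark in section 5 is unsupported, but supplying its inputs or deleting it would change no result.
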